9.3. Analysis Sets

1. Full analysis set.

The full analysis set includes all enrolled participants.

"Enrolled" means a participant's, or their legally authorized representative's, agreement to participate in a clinical study following completion of the informed consent process. Potential participants who are screened for the purpose of determining eligibility for the study, but do not participate in the study, are not considered enrolled, unless otherwise specified by the protocol.

2. Safety analysis set.

The safety analysis set includes all enrolled participants who receive at least one dose of study intervention. Unless otherwise specified, the safety analysis set will be the default analysis set used for all analyses.

3. Per protocol analysis set (evaluable for MTD).

The per protocol analysis set includes all enrolled and evaluable participants who had at least one dose of study treatment and either experienced DLT or do not have major treatment deviations during the DLT observation period.

4. mITT Population.

The mITT is the analysis population that will follow the ITT principle and include participants receiving at least 1 dose of study medication with baseline assessment and at least 1 post baseline assessment, disease progression, or death before the first tumor assessment. The mITT population may be used for interim analysis and conference presentations when the study is still ongoing.

5. PK analysis sets.

The PK parameter analysis population is defined as all enrolled participants treated who do not have protocol deviations influencing PK assessment, and have sufficient information to estimate at least 1 of the PK parameters of interest.

The PK concentration population is defined as all enrolled participants who are treated and have at least 1 postdose analyte concentration.

6. Response Evaluable Set.

The response evaluable population will include all participants who received at least one dose of study treatment and had baseline disease assessment and at least one post baseline disease assessment.

7. PD/Biomarker analysis set(s).

The PD/Biomarker analysis population is defined as all enrolled participants with at least 1 of the PD/Biomarkers evaluated at pre and/or post dose.

8. Immunogenicity analysis set.

The immunogenicity analysis set includes all enrolled participants who receive at least one dose of study treatment and have at least one sample tested for ADA.

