9.4.2. Efficacy Analysis

Response Evaluable Set will be used for all response related analyses including ORR, DCR, DOR, PFS, and TTP, and OS.

Tumor response will be presented in the form of participant data listings that include, but are not limited to tumor type, dose on Day 1, tumor response at each visit. In addition, progression date, death date, date of first response and last assessment date, and date of last contact will be listed. A summary of tumor response based on RECIST 1.1 will also be presented.

Progression date, date of first response, last tumor assessment date, date of last contact, and death date will be listed.

The Kaplan-Meier methods will be used to analyze all time to event efficacy endpoints. The efficacy endpoints that will be analyzed in this study are defined as follows:

- ORR is defined as the percentage of participants with a BOR of CR or PR.
- DCR is defined as the percentage of participants with a BOR of CR, PR, non-CR/non PD or SD.
- DOR is defined as the time from first documentation of CR or PR to date of first documentation of PD or death due to any cause, whichever occurs first.
- PFS is defined as time from start date of treatment to the date of first documentation of PD or death due to any cause.
- TTP is defined as the time from start date of treatment to the date of the first documentation of PD.
- OS is defined as the time from start date of treatment to the date of death due to any cause.

The detailed analyses will be described in the SAP. The definition of each response category is provided in [Appendix 11](#).

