3.2. Secondary Endpoint(s)

3.2.1. Part 1

- *Single dose: C_{max} , T_{max} , AUC_{tau} . If data permits, AUC_{inf} , CL/F , $t_{1/2}$.*
- *Multiple Dose: $C_{max,ss}$, $T_{max,ss}$, $AUC_{tau,ss}$. If data permits, CL_{ss}/F , $t_{1/2,ss}$, and Rac .*
- *C_{trough} at selected time points.*
- *Incidence, titers and endogenous IL-15 cross reactivity of ADA and NAb against PF-07209960.*
- *ORR, DCR as assessed using the RECIST version 1.1.*
- *Time-to-event endpoints: DOR, PFS, and TTP by RECIST version 1.1.*

3.2.2. Part 2

- *Single dose: C_{max} , T_{max} , AUC_{tau} . If data permits, AUC_{inf} , CL/F , $t_{1/2}$.*
- *Multiple Dose: $C_{max,ss}$, $T_{max,ss}$, $AUC_{tau,ss}$. If data permits, CL_{ss}/F , $t_{1/2,ss}$, and Rac .*
- *C_{trough} at selected time points.*

- *Incidence, titers and endogenous IL-15 cross reactivity of ADA and NAb against PF-07209960.*
- *Intra-tumor T cells (such as by CDS IHC) in on-treatment versus baseline tumor biopsy samples.*
- *DCR, DOR, PFS, and TTP by RECISTversion 1.1.*
- *Overall survival.*

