4. ANALYSIS SETS (POPULATIONS FOR ANALYSIS)

Data for all participants will be assessed to determine if participants meet the criteria for inclusion in each analysis population prior to unblinding and releasing the database and classifications will be documented per standard operating procedures.

Table 2. Analysis Sets

Population	Description
Full analysis set	The full analysis set includes all enrolled participants. "Enrolled" means a participant's, or their legally authorized representative's, agreement to participate in a clinical study following completion of the informed consent process. Potential participants who are screened for the purpose of determining eligibility for the study, but do not participate in the study, are not considered enrolled, unless otherwise specified by the protocol.
Safety analysis set	The safety analysis set includes all enrolled participants who receive at least one dose of study intervention. Unless otherwise specified the safety analysis set will be the default analysis set used for all analyses.
Per protocol analysis set (Evaluable for MTD)	The per protocol analysis set includes all enrolled participants who had at least one dose of study treatment and either experienced DLT or do not have major treatment deviations during the DLT observation period. To be DLT evaluable, a participant must have received at least 75% of their planned doses in each cycle for the first two cycles (i.e., ≥ 11 doses received in each of the first two cycles) and has received all scheduled safety assessments during the DLT window.
Modified Intent to Treat (mITT)	The modified intent to treat (mITT) is the analysis population that will follow the ITT principle and include participants receiving at least 1 dose of study medication with baseline assessment and at least 1 post baseline assessment, disease progression, or death before the first tumor assessment. The mITT population may be used for interim analysis and conference presentations when the study is still ongoing.
PK analysis sets	The PK parameter analysis population is defined as all enrolled participants treated who do not have protocol deviations influencing PK assessment, and have sufficient information to estimate at least 1 of the PK parameters of interest.

Population	Description

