	The PK concentration population is defined as all enrolled participants who are treated and have at least 1 postdose analyte concentration.
Response Evaluable set	The response evaluable population will include all participants who received at least one dose of study treatment and had measurable disease at baseline and at least one post baseline disease assessment.
PD/Biomarker analysis set(s)	The PD/Biomarker analysis population is defined as all enrolled participants with at least 1 of the PD/Biomarkers evaluated at pre and/or post dose.
Immunogenicity analysis set	The immunogenicity analysis set includes all enrolled participants who receive at least one dose of study treatment and have at least one sample tested for ADA.

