6.2.3. Tumor Response

- Analysis set: Response evaluable set

- Analysis methodology:
 - For treatment response, 'start date' is defined as the first date that a participant received the study intervention.
 - Overall Response Rate (ORR)
 - ORR as assessed using RECIST version 1.1. ORR is defined as the proportion of participants who achieved CR or PR per RECIST version 1.1 (details are provided in the protocol, Section 8.1.1 and Appendix). Both confirmed ORR and uORR will be determined based on the confirmed and unconfirmed CR and PR, definitions provided below.
 - Disease Control Rate (DCR)
 - A participant with a BOR of CR, PR, non-CR/non-PD or SD is defined as having DC. The DC rate is defined as the percentage of participants with DC in the specified analysis set.
 - Best Overall Response (BOR)
 - **Complete Response (CR):** Two objective assessments of CR a minimum of 4 weeks apart documented before PD.
 - **Partial Response (PR):** Two objective statuses of PR or better (PR followed by PR or PR followed by CR) a minimum of 4 weeks apart documented before PD, but not qualifying as CR. Sequences of PR- Stable- PR are considered PRs as long as the two PR responses are observed at a minimum of 4 weeks apart.
 - **Stable Disease (SD)** (applicable only to participants with measurable disease at baseline): At least one objective status of stable disease or better documented at least 6 weeks after 'start date' and before PD but not qualifying as CR or PR.
 - **Non-CR/non-PD** (applicable only to participants with non-measurable disease at baseline): at least one non-CR/non-PD assessment (or better) documented at least 6 weeks after 'start date' and before first documentation of PD (and not qualifying for CR or PR).
 - **Progressive Disease (PD):** Progression documented within 16 weeks after 'start date' and not qualifying as CR, PR or SD.
 - **Not Evaluable (NE):** All other cases. Note that reasons for NE should be summarized and the following reasons could be used:
 - No adequate baseline assessment (defined below).

- No evidence of disease at baseline.
- No post-baseline assessments due to early death, i.e., death prior to 8 weeks after ‘start date’.
- No post-baseline assessments due to other reasons (adequate post-baseline assessments defined below).
- All post-baseline assessments have overall response NE.
- New anti-cancer therapy started before first post-baseline assessment.

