6.4.3. Overall Response Rate (ORR)

ORR will be determined and summarized in Part 2 in the same fashion as Part 1, which is detailed in Section 6.2.3.

6.5. Secondary Endpoints for Part 2

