6.5.5. Overall Survival

OS will be determined and summarized in Part 2 in the same fashion as Part 1, which is detailed in Section [6.2.3](#).

6.6. Exploratory Endpoints for Part 2

CCI

[REDACTED]

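### ORR, DCR and PFS (and OS, if the protocol governs) are analysed only in participants with a post-baseline disease assessment, so unscanned early deaths drop out; the documents conflict on the set for OS

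*SAP*

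**What the plan says.** **The set.** Protocol 9.3 defines the Response Evaluable set as treated participants who "had baseline disease assessment and at least one post baseline disease assessment". SAP section 4, Table 2 requires that they "received at least one dose of study treatment and had measurable disease at baseline and at least one post baseline disease assessment". Neither definition makes an exception for death or progression before the first scan.

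**Where it is used.** Protocol 9.4.2: "Response Evaluable Set will be used for all response related analyses including ORR, DCR, DOR, PFS, and TTP, and OS". SAP 6.2.3 (ORR, DCR, best overall response) and SAP 6.2.4 (DOR, PFS, TTP) name the same set. SAP 6.4.3 carries it to the Part 2 primary endpoint: "ORR will be determined and summarized in Part 2 in the same fashion as Part 1".

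**OS.** SAP 6.5.5: "OS will be determined and summarized in Part 2 in the same fashion as Part 1", with a pointer to 6.2.3. SAP 3.2 lists "Overall survival" for Part 2 only, and 6.2.3 has no OS text. The fallback in SAP Table 2 is: "Unless otherwise specified the safety analysis set will be the default analysis set used for all analyses".

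**mITT.** Both documents define an mITT set that keeps participants with progression or death before the first tumor assessment. Its use is optional, interim analysis and conference presentations are the only uses named, and no final analysis is assigned to it.

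**The concern.** A treated participant who dies before any scan is a failure for ORR, DCR, PFS and OS. Requiring a scan removes that failure from the denominator or the risk set.

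The SAP's own text does not fit this. On best overall response, 6.2.3 says that "reasons for NE should be summarized and the following reasons could be used", and one reason offered is early death without a post-baseline assessment. Nobody with that reason can be in the set. SAP Table 3 counts a death within 16 weeks of first dose as a PFS event, but an unscanned death is removed before the rule can apply.

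ORR is a Part 2 primary endpoint. Protocol 9.2.2 also plans posterior probabilities of ORR by indication and possible early closure of a cohort, so the denominator feeds real judgements even though nothing is formally tested.

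**Working it through.** **1. The plan's own figures.** With the Jeffreys prior, the posterior for x responders of n is Beta(x + 0.5, n - x + 0.5). For 5/20 this gives P(ORR > 20%) = 0.725, as printed in protocol 9.2.2; 1/10 gives 0.774 for ORR at or below 20%, against the printed 0.77. All 12 rows of protocol Table 5 reproduce to within 0.001.

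**2. ORR.** If m of n treated participants have no scan, none of them is a responder, so x/n is reported as x/(n - m). The ratio n/(n - m) is never below 1. Intervals are Clopper-Pearson (SAP 5.2.1).

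| Treated | Responders | Lost | ORR (95% CI) | P(ORR > 20%) |
|---|---|---|---|---|
| 20 | 4 | 0 | 20.0% (5.7-43.7) | 0.523 |
| 20 | 4 | 1 | 21.1% (6.1-45.6) | 0.568 |
| 20 | 4 | 2 | 22.2% (6.4-47.6) | 0.615 |
| 30 | 6 | 0 | 20.0% (7.7-38.6) | 0.519 |
| 30 | 6 | 2 | 21.4% (8.3-41.0) | 0.593 |
| 30 | 6 | 3 | 22.2% (8.6-42.3) | 0.630 |

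**3. How many might be lost.** The documents do not say. Assume exponential OS with median M of 6 to 12 months. The first scan is at 8 weeks, t0 = 1.84 months. Deaths before it: d = 1 - exp(-ln2 × t0/M) = 19.1% (M = 6) or 10.1% (M = 12). Assume also that half are unscanned: f = d/2 = 9.6% or 5.0%, which is 1.9 or 1.0 of 20, and 2.9 or 1.5 of 30. The true share may be near zero, because protocol 8.1.1 requires imaging whenever progression is suspected. At the other extreme, losing 4 of 20 needs essentially every death before week 8 to be unscanned at M = 6 (0.191 × 20 = 3.8). ORR would then read 4/16 = 25.0%, with P(ORR > 20%) = 0.708.

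**4. DCR.** The same ratio applies. An assumed 10/20 = 50.0% reads as 10/19 = 52.6% or 10/18 = 55.6%.

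**5. PFS.** Only unscanned deaths that Table 3 would count matter, chiefly those within 16 weeks of first dose. Participants who stop alive without a scan would be censored at first dose and add essentially nothing. Beyond week 8, an assumed PFS of 30% reads as 0.30/(1 - f) = 31.6% to 33.2%.

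**6. OS, if the protocol governs.** Removing a fraction f, all early deaths, moves the median to M × (ln2 - ln(1 - f))/ln2. For M = 6 this is 6.87 months (+14.5%); for M = 12 it is 12.90 (+7.5%). If no early death goes unscanned, the shift from this source is nil. Participants who stop alive without a scan remain in survival follow-up (protocol 7.1); dropping them could move OS either way and is not modelled.

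**7. TTP and DOR.** TTP censors deaths, and SAP Table 4 would censor an unscanned participant at first dose. DOR covers responders, who all have scans. Neither is materially affected.

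**8. DCR in Part 1.** DCR counts non-CR/non-PD, which SAP 6.2.3 reserves for non-measurable disease. The SAP set requires measurable disease, so the category is empty there; under the protocol's definition it is not.

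**The case against.** The case on the other side is substantial.

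- **The loss may be very small.** Scans are required on suspected progression and at withdrawal if none was done in the previous 6 weeks (protocol 8.1.1), and standard-of-care imaging after end of treatment is still reported (protocol 1.3.2). Many who stop early can enter the set. This stands, and is why the lower end is zero.
- **A suitable set exists.** The mITT set keeps early deaths. This stands only in part: it is optional and tied to no final analysis.
- **OS is not settled.** A reader might infer that the plan has chosen to condition OS on a scan. The documents do not support that. The SAP may modify the protocol (protocol section 9), its default is the safety set, and SAP Table 5 censors OS at last contact without reference to scans. The pointer in 6.5.5 looks like a cross-reference slip, since 6.5.4 likewise sends DOR, PFS and TTP to 6.2.3 although they sit in 6.2.4. What the documents show is a conflict.
- **The list of NE reasons proves little about intent.** It also includes no evidence of disease at baseline, which is equally impossible in this set. It may be template text. It still has to be reconciled.
- **Nothing is tested, and much is recoverable.** SAP 5.1 has no formal Part 2 decision rules. SAP 6.8.2 tabulates set membership, so all-treated ORR can be rebuilt; deaths are listed (SAP 6.9.1) and individual time-to-event data presented (SAP 5.2.4). This limits the harm, but the reported estimates still use the narrower denominator.
- **Restricting ORR to measurable disease is defensible.** Agreed: protocol Appendix 11 gives no PR category for non-target-only disease.

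**Conclusion.** The point holds for ORR, DCR and PFS as written in both documents. For OS it holds as a conflict between protocol 9.4.2, SAP 6.5.5 and the SAP default.

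The direction is certain for ORR and DCR. For PFS it follows from the loss of unscanned deaths alone. Conditioning OS on a scan would overstate it to the extent that those excluded are early deaths.

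The size is illustrative. It rests on several assumptions, none from the documents: exponential OS, a 6 to 12 month median, half of early deaths unscanned, and the DCR and PFS levels used. A reader might infer from the posterior probabilities or the OS percentages that a cohort's result would be materially distorted. That is not supported. A 1 to 2 point shift in ORR at 4/20 compares with an interval about 38 points wide (43.7 - 5.7). Under the exponential model, 20 observed deaths give a 95% interval for median OS of about 0.67 to 1.64 times the estimate, so a 7.5% to 14.5% shift lies well inside it. It should be fixed because the error tends one way and costs little to remove, not because it would overturn a conclusion.

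**What to change.** - **OS and PFS:** analyse in the safety analysis set (all treated).
- **ORR and DCR:** analyse in all treated participants with the baseline disease that the endpoint requires. Count no post-baseline assessment as a best overall response of NE, that is, non-response. Keep the Response Evaluable set as supportive.
- **Part 2 posterior probabilities:** use the same denominator for the final calculation. Reconcile it with protocol 9.2.2, which bases its early-closure example on the first 10 evaluable participants but times the assessment by the number enrolled.
- **SAP 6.5.5:** name the OS analysis set and point to Table 5 of SAP Appendix 1.
- **Set definition:** reconcile measurable disease (SAP Table 2) with baseline disease assessment (protocol 9.3) for DCR. ORR may stay limited to measurable disease.
- **TTP and DOR:** no change.

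Cost: wording in SAP Table 2, 6.2.3, 6.2.4 and 6.5.5 and in protocol 9.2.2 and 9.4.2. No new data are needed. Since ORR is a Part 2 primary endpoint, protocol section 9 calls for a protocol amendment if the change counts as major. The downside is that reported ORR, DCR and PFS, and probably OS, become slightly less favourable.

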5. GENERAL METHODOLOGY AND CONVENTIONS

5.1. Hypotheses and Decision Rules

There will be no formal hypothesis testing in this study.

Decision Rules for Part 1:

Dosing decisions during dose escalation will be based on the following:

The dose escalation in the Part 1 of the study will be guided by a Bayesian analysis of DLT data for PF-07209960. Dose toxicity is modelled using two-parameter logistic regression for the probability of a participant experiencing a DLT at the given dose.

Assessment of Participant Risk:

After each cohort of participants, the posterior distribution for the risk of DLT for new participants at different doses of interest for PF-07209960 will be evaluated. The posterior distributions will be summarized to provide the posterior probability that the risk of DLT lies within the following intervals:

Under-dosing	[0, 0.16)
Targeted dosing	[0.16, 0.33)
Overdosing	[0.33, 1]

The EWOC principle:

Dosing decisions are guided by the escalation with overdose control principal (Rogatko et al, 2007). A dose may only be used for newly enrolled participants if the probability of overdosing at that dose is CCI.

Recommendation from the BLRM, along with safety (AEs, SAEs), laboratory, PK, biomarker and other relevant data, will be used at the time of each dose escalation and for MTD/RP2D determination.

Prior distributions:

Weakly informative prior distributions based on pre-clinical/expert opinion information will be chosen for the logistic parameters, see Appendix 8 in the protocol.

Starting dose:

The starting dose is CCI in Part I Dose Escalation. For this dose the prior risk of overdosing satisfies the EWOC criterion.

Stopping Criteria:

The dose escalation will be stopped when the following criteria are met:

- *At least 6 participants have been treated at the recommended MTD/RP2D.*
- *The dose d^\sim satisfies 1 of the following conditions:*
 - *The probability (π) of target toxicity at dose d^\sim exceeds 50%, ie, $Pr(0.16 \leq rr_{d^\sim} < 0.33) \geq 50\%$.*
 - *A minimum of 15 participants have been treated in the trial.*

In case all doses explored appear to be overly toxic and the MTD cannot be determined, the dose escalation will stop.

In case of change of the dosing regimen, DLT data accumulated during the dose escalation with the original regimen might be used to form a MAP prior for further BLRM analysis. MAP priors are derived from hierarchical models, which take into account possible differences between the studies. Details of priors and general description of MAP approach is presented in see Appendix 8 in the protocol and a statistical technical supplement.

To mitigate the risk of misclassifying DLTs, a sensitivity that uses weighted DLT/AE data (in equivocal cases) within the BLRM will be performed. If all investigators and the sponsor agree on the equivocal DLT/AE data, the DLT weighting approach could be the primary dose escalation method (see Appendix 8 in the protocol).

Decision Rules for Part 2:

The primary objective in dose expansion is to further characterize the safety and preliminary efficacy profile of PF-07209960. There are no formal decision rules and summary statistics will be provided for safety and efficacy endpoints.

5.2. General Methods

Every effort has been made to pre-specify all analyses in this SAP. The SAP will be amended if additional exploratory analyses are deemed necessary that were not initially specified.

The data are summarized by dose level cohort, defined by the initial dose of the study intervention administered to participants. DLT rates at the study dose levels will be presented via mean and medians and a Bayesian credible interval based on the posterior density from the full probability model. This information will also be used for DLRM to guide dose escalation.

For Part 1, unless otherwise specified, all other summaries will be presented by dose level cohort and overall. For Part 2 unless otherwise specified, all other summaries will be presented by expansion cohort. Additionally, summary tables will include the total sample size and number missing/not reported. Lastly, missing data may be imputed according to Section 5.3 and unless otherwise specified missing values that are not imputed will be excluded from the analysis.

